	
Summary measure: Difference of the overall mean monthly 50% response rate across the 3-month double-blind treatment period between treatment groups

Primary Sensitivity 3	
To assess whether galcanezumab is superior to rimegepant in the prevention of migraine in participants with episodic migraine	
Treatment condition: Galcanezumab injections of 120 mg SC or rimegepant 75 mg ODT regardless of initiation of new preventive migraine medication, regardless the use of acute medication to treat an acute migraine attack and regardless of discontinuing treatment due to any reason (treatment policy strategy)

	
Population: Participants who meet IHS-ICHD-3 (2018) criteria for a diagnosis of migraine with or without aura with an episodic frequency of 4 to 14 migraine headache days per month and fulfils the inclusion and exclusion criteria of the study. (This population will not include participants that take acute medication and do not meet the migraine headache criteria at baseline.)

	
Variable (endpoint):

Document: **CCI**Author: **PPD**

Version Number:

3.0

Version Date:

19May2023

Objective	Estimands
	
The percentage of participants with $\geq 50\%$ reduction from baseline in monthly migraine headache days across the 3-month double-blind treatment period

	
Remaining intercurrent event handling: A migraine headache day will be considered when the participant takes acute medication regardless if the headache does not meet the criteria of migraine. This analysis will consider if a participant uses an acute medication (triptans or ergot derivatives) – as reported in the CM_AHM eCRF, regardless of whether a headache was reported. Subjects using a Triptan and/or ergot derivative will be identified by medical review of the eCRF.

	
Summary measure: Difference of the overall mean monthly 50% response rate across the 3-month double-blind period between treatment groups

Primary Sensitivity 4	

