To compare galcanezumab with rimegepant with respect to monthly migraine headache days	
Treatment condition: Galcanezumab injections of 120 mg SC or rimegepant 75 mg ODT, regardless of initiation of new preventive migraine medication, regardless the use of acute medication to treat an acute migraine attack and regardless of discontinuing treatment due to any reason (treatment policy strategy)
 
Population: Participants who meet IHS-ICHD-3 (2018) criteria for a diagnosis of migraine with or without aura with an episodic frequency of 4 to 14 migraine headache days per month and fulfills the inclusion and exclusion criteria of the study.
 
Variable (endpoint): The overall mean change from baseline in the number of monthly migraine headache days across the 3-month double-blind treatment period
 
Remaining intercurrent event handling: To assess the robustness of the primary analysis conclusions to

Document: CCI

Author: PPD

Version Number: 3.0

Version Date: 19May2023

Objective	Estimands
	
deviations from missing at random (MAR) assumption, this analysis will vary the assumptions of missing data for the primary analysis in a systematic way.

	
Summary measure: Difference of the overall mean change from baseline in the number of monthly migraine headache days across the 3-month double-blind treatment period

Key Secondary	
To compare galcanezumab with rimegepant with respect to monthly migraine headache days	
Treatment condition: Galcanezumab injections of 120 mg SC or rimegepant 75 mg ODT, regardless of initiation of new preventive migraine medication, regardless the use of acute medication to treat an acute migraine attack and regardless of discontinuing treatment due to any reason (treatment policy strategy)

	
Population: Participants who meet IHS-ICHD-3 (2018) criteria for a diagnosis of migraine with or without aura with an episodic frequency of 4 to 14 migraine headache days per month and fulfils the inclusion and exclusion criteria of the study.

	
Variable (endpoint): The overall mean change from baseline in the number of monthly migraine headache days across the 3-month double-blind treatment period

	
Remaining intercurrent event handling: NA

	
Summary measure: Difference of the overall mean change from baseline in the number of monthly migraine headache days across the 3-month double-blind treatment period

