18.2.3. PRIMARY ANALYSIS OF PRIMARY EFFICACY VARIABLE(S)

The primary objective of this study is to assess whether galcanezumab is superior to rimegepant in the prevention of migraine in participants with episodic migraine. The primary estimand of interest is the overall mean monthly 50% response rate across the 3-month double-blind period attributable to the randomized treatment based on all available data as estimated from the model based on GLIMMIX-procedure. All available monthly migraine headache data will contribute to analysis as long as baseline monthly migraine headache day values are available. Any migraine headache day data collected after study intervention discontinuation but within the double-blind period will still be used within the analysis.

The primary efficacy analysis will be performed for the ITT. This endpoint (50% responder) is binary variable with repeated measures and will be analyzed using a GLIMMIX procedure as pseudo-likelihood-based mixed effects repeated measures analysis. The GLIMMIX procedure will include the fixed, categorical effects of treatment, month, and treatment-by-month interaction, as well as the continuous, fixed covariate of baseline monthly migraine headache days value. Binary distribution and logit link will be used.

An unstructured covariance structure will be used to model the within-participant errors (denoted by TYPE=CHOL in the RANDOM statement). The Newton-Raphson method with ridging will

Document: **CCI**

Author: **PPD**

Version Number:

3.0

Version Date:

19May2023

CCI

be used for nonlinear optimization (denoted by including NLOPTIONS TECH=NRRIDG). The Kenward-Roger (Kenward and Roger 1997) approximation will be used to estimate denominator degrees of freedom. If the model does not converge, the Fisher scoring algorithm will be utilized by the SCORING option in SAS.

If the model still fails to converge, the model will be fit using covariance matrices in the following order specified by a decreasing number of covariance parameters until convergence is met:

- Heterogeneous Toeplitz,
- Heterogeneous autoregressive,
- Toeplitz, and
- Autoregressive.

If necessary, both fitting algorithms will be used in the pre-specified order before proceeding to the next covariance structure in the sequence.

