18.2.4. SENSITIVITY ANALYSIS OF PRIMARY EFFICACY VARIABLE(S)

The following sensitivity analyses are of the primary efficacy variable are planned:

- I) To consider the case where to discard the data of the participants that discontinue treatment and may have different expectations regarding efficacy of the two treatments such as the onset of effect given the different dosing and mode of administration of the comparators. For such analyses, the data after whichever of the following is sooner will be discarded: the date of the last injection+30 days or the

Document:

CCI

Author:

PPD

Version Number:

3.0

Version Date:

19May2023

date of the last oral administration +1 day.

- II) To consider participants that withdraw for lack of efficacy or tolerability, or participants that switch preventive treatment as no responders (composite strategy).
- III) To consider a migraine headache day when the participant takes acute medication regardless of the headache does not meet the criteria of migraine. This analysis will consider if a participant uses an acute medication (triptans or ergot derivatives) – as reported in the CRF (CM_AHM), regardless of whether a headache was reported. For this analysis baseline and post-baseline ‘migraine headache days’ need to be defined using the reporting of medications in CM_AHM CRF. Input from clinical will be used to help identify the classes of acute medication used.
- IV) To assess the robustness of the primary analysis conclusions to deviations from missing at random (MAR) assumption. The approach for these analyses is to vary the assumptions of missing data for the primary analysis in a systematic way. Basically, the method will be to predict the missing outcomes and then add values ($\Delta_{120}, \Delta_{75}$) to the predictions in the Galcanezumab 120 mg and rimegepant 75 mg treatment groups respectively, regardless of the reason the data are missing. This approach is consistent with the sensitivity approach suggested in Permutt (2015). This procedure will be repeated multiple times for different values of ($\Delta_{120}, \Delta_{75}$) using the following steps:
 - 1) Predict the missing outcomes for each treatment via multiple imputation based on observed primary endpoint and baseline values. Such imputation will be carried out using a Markov Chain Monte Carlo method with a Jeffreys prior via SAS® PROC MI. Thirty (30) such imputations will be created.

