 - 2) Add the corresponding Δ value (i.e. $\Delta_{120}, \Delta_{75}$) to the imputed values based on the patient treatment group.
 - 3) Conduct the primary analysis separately for each of the 30 imputations.
 - 4) Combine the results of these analyses using Rubin’s combining rules, as implemented in SAS® PROC MI ANALYZE.

The above steps will be repeated multiple times for different values of ($\Delta_{120}, \Delta_{75}$) with Δ_{75} ranging from 0 to twice the absolute value of the mean value seen for rimegepant in the primary analysis, Δ_{120} ranging from Δ_{75} to $\Delta_{75} + \text{absolute value of the biggest mean treatment difference seen within the primary analysis}$. For example, if the overall mean change from

Document: **CCI**

Author: **PPD**

Version Number:

3.0

Version Date:

19May2023

CCI

baseline for rimegepant is -3.6 and the maximum overall treatment difference is -1.5, then Δ_{75} would range from 0 to 7.2 and Δ_{120} would range from Δ_{75} to $\Delta_{75} + 1.5$.

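### Primary Sensitivity 4, the only analysis stated to vary missing at random for the primary result, is defined on mean change in days in Table E but reruns the binary responder analysis in SAP 18.2.4

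*SAP*

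**What the plan says.** Table E (SAP 2.4) defines four sensitivity estimands for the primary result. The first three keep the responder endpoint; the summary measure of Primary Sensitivity 3, for example, is "Difference of the overall mean monthly 50% response rate across the 3-month double-blind period between treatment groups". Row 4 is meant to test robustness to departures from missing at random, and says that "this analysis will vary the assumptions of missing data for the primary analysis in a systematic way". Its variable, however, is continuous: "The overall mean change from baseline in the number of monthly migraine headache days across the 3-month double-blind treatment period". Its objective, variable and summary measure match those of the first key secondary row, which SAP 7.4 tests as H02.

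SAP 18.2.4 opens with "The following sensitivity analyses are of the primary efficacy variable are planned" and describes the same analysis as item IV. Step 1 reads "Predict the missing outcomes for each treatment via multiple imputation based on observed primary endpoint and baseline values". Step 2 adds a treatment-specific delta to the imputed values. Step 3 reads "Conduct the primary analysis separately for each of the 30 imputations". That primary analysis is the GLIMMIX model of SAP 18.2.3, for which "Binary distribution and logit link will be used".

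The rimegepant delta runs from 0 to "twice the absolute value of the mean value seen for rimegepant in the primary analysis". The galcanezumab delta runs from the rimegepant delta to that value plus the largest mean treatment difference. The worked example uses a rimegepant mean change of -3.6 and a treatment difference of -1.5.

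**The concern.** One analysis has two definitions, on different variables and with different models. The one in Table E can be run, but it answers a question about H02. Reporting it as robustness of the primary conclusion would attach the reassurance to the wrong endpoint. The one in SAP 18.2.4 names the right endpoint but takes its deltas from another scale.

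This matters because no other listed analysis is stated to vary missing at random. Sensitivity I discards data after treatment stops. Sensitivity III redefines a migraine day. Sensitivity II sets some participants to non-response, but only those who withdraw for lack of efficacy or tolerability or who switch preventive treatment. Other losses, and months set to missing because diary compliance was 50% or less (SAP 18.1.2), would have no such check on the 50% response endpoint.

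**Working it through.** **1. The plan's own delta range.** 2 × |-3.6| = 7.2 and |-1.5| = 1.5, so the rimegepant delta runs from 0 to 7.2 and the largest galcanezumab delta is 7.2 + 1.5 = 8.7. This reproduces the example, but only with mean changes in days. Those come from the MMRM for H02 (SAP 18.3.2.2), not from the primary model.

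**2. The same rule on the response scale.** The documents give no response rates, so assume 30% to 60% for rimegepant and add the planned 12 points (SAP 3.1.1).
- The rimegepant delta reaches 2 × 0.30 = 0.60 to 2 × 0.60 = 1.20. The galcanezumab delta reaches 0.72 to 1.32.
- The shifted galcanezumab rate becomes 0.42 + 0.72 = 1.14 up to 0.72 + 1.32 = 2.04. Both exceed 1.
- A 0/1 value plus a fractional delta is no longer binary, so the model in step 3 cannot be fitted to it.
- The sign reverses. More days is worse, but more response is better. With assumed rates of 44% and 56%, 10% missing, and deltas of 0 (rimegepant) and 0.12 (galcanezumab), the difference is 0.9 × 12 + 0.1 × (68 - 44) = 13.2 points. The intended stress test would widen the effect.

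**3. Size on the days scale (Table E reading).** Let mG and mR be the assumed shares of missing months, and start from the SAP's example difference of 1.5 days. What remains is 1.5 minus the maximum of [mG × delta120 - mR × delta75]. With delta120 = delta75 + e, the bracket is (mG - mR) × delta75 + mG × e, where e runs from 0 to 1.5.
- 5%/5%: 1.5 - 0.05 × 1.5 = 1.425
- 10%/10%: 1.5 - 0.10 × 1.5 = 1.35
- 12%/8%: 1.5 - (0.04 × 7.2 + 0.12 × 1.5) = 1.032
- 8%/12%: 1.5 - 0.08 × 1.5 = 1.38 (worst at delta75 = 0)

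**4. Size on the responder scale (days shifted, then classified).** All of the following are assumptions:
- baseline truncated normal on 4 to 14 days, mean 8.2, 8.65 or 9.0 (SD 2.9 before truncation);
- monthly change normal, SD 3.0, 3.5 or 4.0;
- rimegepant mean change -3.3, -3.6 or -4.2, constant or proportional to baseline;
- galcanezumab mean solved to give 12 points more response, which needs 0.9 to 1.3 days and implies 35% to 51% rimegepant response.

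Response means change ≤ -0.5 × baseline. The remaining difference is (1 - mG)pG + mG·pG(delta120) - (1 - mR)pR - mR·pR(delta75), minimised over the SAP's grid.

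| Missing months, galcanezumab/rimegepant | Cap on delta120 - delta75 = solved day difference | Cap = 1.5 days | Days scale (step 3) |
|---|---|---|---|
| 5%/5% | 11.4 points | 11.0 to 11.3 | 1.425 days |
| 10%/10% | 10.8 | 10.0 to 10.6 | 1.35 |
| 12%/8% | 8.5 to 9.2 | 8.5 to 9.2 | 1.032 |
| 8%/12% | 11.0 | 10.4 to 10.9 | 1.38 |

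Two hand checks agree. At 10%/10% with the solved cap, missing galcanezumab months fall to the rimegepant rate, leaving 12 - 0.10 × 12 = 10.8. At 12%/8% with large deltas, almost no shifted month responds, leaving about 0.88 × (pR + 0.12) - 0.92 × pR = 0.1056 - 0.04 × pR. That is 9.2 points at pR = 0.35 and 8.5 at pR = 0.51.

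**The case against.** The best reply is that the intent can be inferred. The worked example in item IV is in days, as in Table E, and adding deltas to values drawn by MCMC suits a continuous outcome. SAP 18.1.1 itself calls the percent reduction in days the primary measure and derives responder status from it, and SAP 18.2.1 refers to that section. Imputing days and then classifying is therefore a natural reading. This stands as an account of what may have been meant. It does not cure the text, because item IV never states that step and Table E's summary measure contradicts its result, which would be a response-rate difference.

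It can also be said that the choice hardly changes the message. Under the assumptions above, the share of effect kept is similar on the days and responder scales: 95% against 92 to 95% at 5%/5%, 90% against 84 to 90% at 10%/10%, 69% against 71 to 77% at 12%/8%, and 92% against 87 to 92% at 8%/12%. This is fair, and it is why no changed conclusion is predicted. But the agreement rests on an assumed model, and a days result still cannot be reported as a result for the 50% endpoint.

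Three further points stand as limits. Sensitivity II does depart from missing at random for some informative withdrawals. The 10% dropout ceiling counts participants, so the missing-month shares are not derived from it. The output templates mentioned in SAP section 8 are not in the documents given and may show which variable is intended, though they would not remove the conflict within the SAP text.

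**Conclusion.** The point holds. Table E and SAP 18.2.4 item IV define the same analysis on different outcomes, and item IV mixes scales within itself. Followed as written, Table E leaves the 50% response result with no delta analysis of missing at random, only the partial cover of Sensitivity II. The primary test, its alpha and the testing hierarchy are not affected, and nothing here shows that the primary conclusion would change.

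In the illustration, the smallest remaining difference from 12 points is 10.0 to 11.4 when missingness is equal at 5% or 10%. It is 8.5 to 9.2 when galcanezumab has more missing months (12%/8%) and 10.4 to 11.0 in the reverse case. Those sizes rest on assumed missing shares, baseline distribution, SDs and mean changes; the documents supply only the 12-point difference, the 10% dropout ceiling and the delta rule. The mismatch itself rests on the text alone. It should be corrected before the SAP is final.

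**What to change.** In Table E, give Primary Sensitivity 4 the objective, variable and summary measure of the primary estimand (50% response).

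In SAP 18.2.4, item IV, state that deltas are in migraine headache days, that positive means worse, and that their bounds come from the H02 MMRM estimates. Then write the steps in order:
1. Impute missing monthly migraine headache days.
2. Add delta to the imputed values.
3. Derive 50% responder status by the rule in SAP 18.1.1.
4. Run the primary GLIMMIX on each of the 30 completed data sets.
5. Combine by Rubin's rules.

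State that imputed values are not truncated before the shift. After it, values below 0 or above 30 days need no rule for this endpoint: with a baseline of 4 to 14 days, they classify as response and non-response in any case.

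Keep the mean-change version, labelled as a sensitivity analysis of H02. The cost is SAP wording and one derivation step in the program, with no new data.

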3. STUDY DESIGN

3.1. GENERAL DESCRIPTION

Study CGBD is a multi-site, randomized, double-blind, double-dummy, parallel-group, Phase 4 study with 3 study periods in participants who meet IHS-ICHD-3 (2018) criteria for a diagnosis of migraine with or without aura with an episodic frequency of 4 to 14 migraine headache days per month. For additional details about each study period see section 4.1 of the protocol.

Treatments:

- Galcanezumab 120 mg subcutaneous (SC) once monthly, with a 240 mg loading dose as the initial dose
- Rimegepant 75 mg orally disintegrating tablet (ODT) every other day

Participants will be given placebo in a double-dummy design. Randomization will be stratified by baseline migraine frequency (<8 migraine headache days versus ≥ 8 migraine headache days).

Document: CCI

Author: PPD

Version Number:

[figure not shown]
3.0

Version Date:

19May2023

CCI

Figure A: Schema

Abbreviations: ODT = oral disintegrating tablet; QM = every month; QOD = every other day; SC = subcutaneous; SP = Study Period.

- a Screening Period is 3-30 days in length.
- b Eligibility is determined between a minimum of 30 days and a maximum of 40 days. Investigators have up to 5 additional days, if needed, to schedule participant's Visit 3 appointment.
- c Randomization occurs at Visit 3. Participants randomized to galcanezumab will receive a loading dose of 240 mg at the first administration only.

Note: Participants will be given placebo in a double-dummy design.

3.1.1. SAMPLE SIZE DETERMINATION

The study will screen an estimated 1150 potential study participants to ensure a minimum of approximately 575 randomized participants. Based on the assumption of treatment difference of 12%, the minimum sample size of approximately 575 provides more than 85% power at a two-sided significance level of 5% and a dropout rate of no more than 10%, with the opportunity to increase the final sample size at the interim analysis if indicated to maintain a well-powered

Document: **CCI**

Author: **PPD**

Version Number:

3.0

Version Date:

19May2023

CCI

study. To preserve blinding, details of the sample size and power calculations are omitted from the protocol and are provided to the ERB in a separate document. If the interim is not performed, then the trial will enroll to a sample size as specified in the ERB document.

3.2. SCHEDULE OF ACTIVITIES

Schedule of activities (SoA) can be found in Section 1.3 of the protocol.

3.3. CHANGES TO ANALYSIS FROM PROTOCOL

In addition to the exploratory objectives and endpoints specified in the protocol, this SAP contains additional exploratory objectives and endpoints to assess onset of action, sustained response, and other endpoints of interest. See Section 2.3 for details.

4. PLANNED ANALYSES

The following analyses will be performed for this study:

- Interim Analysis
- Final Analysis

4.1. DATA MONITORING COMMITTEE

There will be no DMC for this study.

4.2. INTERIM ANALYSIS

One interim analysis is planned for this study. The interim analysis will occur during Study Period III (double-blind treatment); this may result in increasing the sample size or continuing with the planned sample size. Details will be documented in a separate Statistical Analysis Center (SAC) SAP and ERB supplement.

To minimize the potential bias that results from performing an interim analysis, the interim analysis for this study will be conducted by a SAC external to the study team, but internal to Lilly.

Only the SAC is authorized to evaluate unblinded interim analyses results to make an informed

Document: CCI

Author: PPD

Version Number:

3.0

Version Date:

19May2023

CCI

decision. Study sites will receive information about interim results ONLY if they need to know for the safety of their patients.

Unblinding details will be specified in a separate unblinding plan document or in the unblinding plan section of the SAC SAP.

4.3. FINAL ANALYSIS

All final, planned analyses identified in this SAP will be performed by IQVIA Biostatistics following Sponsor Authorization of this Statistical Analysis Plan, Database Lock, Sponsor Authorization of Analysis Sets and Unblinding of Treatment.

5. ANALYSIS SETS

Agreement and authorization of participants included/excluded from each analysis set will be conducted prior to the unblinding of the study. Unless otherwise specified, all analyses will be conducted according to the ITT principle on the ITT population. That is, participants will be analyzed according to the treatment they were randomized, regardless of whether they actually received a different treatment.

5.1. INTENTION TO TREAT (ITT) SET

The Intention to Treat (ITT) set will contain all randomized participants who receive at least 1 dose of both study interventions (injection and ODT). Participants will be included in the analyses according to their randomized treatment.

When change from baseline is assessed, the analysis will include participants in the ITT population who have a baseline and a postbaseline measurement.

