## 6. Study Intervention(s) and Concomitant Therapy

Study intervention is defined as any investigational intervention(s), marketed product(s), placebo, or medical device(s) intended to be administered to/used by a study participant according to the study protocol. It is a pharmaceutical form of an active ingredient or placebo being tested or used as a reference in a clinical trial, including a product with a marketing authorization when used or assembled (formulated or packaged) in a way different from the approved form, or when used for an unapproved indication, or when used to gain further information about an approved use (FDA 2018).

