## 9.2. Analyses Sets

Participant Analysis Set	Description
Intention to Treat (ITT) set	All randomized participants and receive at least 1 dose of study intervention. Participants will be included in the analyses according to their randomized treatment.
Safety analysis set	All participants who are exposed to study intervention. Participants will be analyzed according to the treatment they actually received.

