informed consent	A process by which a participant voluntarily confirms his or her willingness to participate in a particular study, after having been informed of all aspects of the study that are relevant to the participant's decision to participate. Informed consent is documented by means of a written, signed and dated informed consent form.
interim analysis	An interim analysis is an analysis of clinical study data, separated into treatment groups, that is conducted before the final reporting database is created/locked.
INR	International normalized ratio
IRB/IEC	Institutional Review Board/Independent Ethics Committee
ITT	Intention to treat: The principle that asserts that the effect of a treatment policy can be best assessed by evaluating on the basis of the intention to treat a participant (that is, the planned treatment regimen) rather than the actual treatment given. It has the consequence that participant allocated to a treatment group should be followed up, assessed, and analyzed as members of that group irrespective of their compliance to the planned course of treatment.
IWRS	Interactive web-response system
LLT	Lowest Level Term
LOCF	Last observation carried forward
LSMeans	Least Squares Means
MedDRA	Medical Dictionary for Regulatory Activities
MMRM	Mixed-model repeated measures
NIMP	Non-investigational Medicinal Product
ODT	Oral disintegrating tablet

participant	Equivalent to CDISC term “subject”: an individual who participates in a clinical trial, either as recipient of an investigational medicinal product or as a control.
PC	Product complaint
P-gp	P-glycoprotein
PK/PD	Pharmacokinetics/Pharmacodynamics
PPS	Per-protocol set: The set of data generated by the subset of participant who sufficiently complied with the protocol to ensure that these data would be likely to exhibit the effects of treatment, according to the underlying scientific model.
PRO/ePRO	Patient-reported outcomes/Electronic patient-reported outcomes
PT-INR	Prothrombin time – international normalized ratio
QOD	Every other day
QTc	Corrected QT interval
QTcF	Fridericia-corrected QT interval
QTLs	Quality tolerance limits
SAC	Statistical Analysis Center
SAE	Serious adverse event
SAP	Statistical analysis plan
SC	Subcutaneous

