5.2. SAFETY ANALYSIS SET (SAF)

The safety analysis set (SAF) will contain all participants who are exposed to study intervention (either injection or ODT). Participants will be analyzed according to the treatment they actually received.

If there is any doubt whether a participant was treated or not, it will be assumed that the

Document: CCI

Author: PPD

Version Number:

3.0

Version Date:

19May2023

CCI

participant has been treated for the purposes of analysis.

When change from baseline is assessed, the participant will be included in the analysis only if the participant has a baseline and a postbaseline measurement.

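### The SAP narrows the ITT set to participants dosed with both injection and tablet, without declaring the change, so some randomised and treated participants can drop out of the primary analysis

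*SAP*

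**What the plan says.** Protocol 9.2 defines the ITT set as "All randomized participants and receive at least 1 dose of study intervention", analysed by randomised treatment. Protocol section 6 explains the term: "Study intervention is defined as any investigational intervention(s), marketed product(s), placebo, or medical device(s) intended to be administered" under the protocol. On that definition a dose of either component of the double dummy, active or placebo, is a dose of study intervention.

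SAP 5.1 defines the ITT set as "all randomized participants who receive at least 1 dose of both study interventions (injection and ODT", again analysed by randomised treatment. SAP 5.2, directly after it, defines the safety set as "all participants who are exposed to study intervention (either injection or ODT".

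SAP 18.2.3 ties the primary result to the narrower set: "The primary efficacy analysis will be performed for the ITT". SAP 3.3 is the place for departures from the protocol, and the only one it reports is that "this SAP contains additional exploratory objectives and endpoints to assess onset of action, sustained response, and other endpoints of interest". The analysis set is not mentioned.

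**The concern.** The SAP adds a second post-randomisation condition for entry to the primary analysis and keeps the ITT label. The contrast between both in 5.1 and either in 5.2 means that one-product participants are kept for safety and removed for efficacy.

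This conflicts with three other statements in the plan:

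- The protocol glossary describes ITT as a principle under which participants are "analyzed as members of that group irrespective of their compliance to the planned course of treatment".
- The primary estimand in SAP 2.4, Table E, is treatment policy: stopping treatment for any reason does not remove a participant.
- Protocol 7.1 keeps participants who stop study intervention under efficacy follow-up, so a one-product participant can supply usable diary data.

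Each arm has one active product and one placebo. Protocol 6.3 describes training on the injection and then on the tablet. If that is the order of dosing, someone who receives the injection and never takes a tablet has had active drug in the galcanezumab arm but only placebo in the rimegepant arm. The reason for stopping could therefore differ by arm, and so could the exclusions.

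The effect is not confined to efficacy. SAP 9.1 and 9.2 tabulate disposition and important protocol deviations on the ITT set, so a treated participant could be missing from those tables while counted in the safety set.

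**Working it through.** **Who is in which set.** Reading protocol 9.2 with the section 6 definition:

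| Doses received at any time | Protocol 9.2 ITT | SAP 5.1 ITT | SAP 5.2 safety set |
|---|---|---|---|
| Injection and tablet | in | in | in |
| Injection only | in | **out** | in |
| Tablet only | in | **out** | in |
| Neither | out | out | out |

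The definitions differ in the two middle rows. No arithmetic is needed to establish the point; the rest concerns its size.

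**The plan's own figure.** Protocol 9.5 and SAP 3.1.1 give about 575 randomised (1:1, so 287.5 per arm), a 12-point difference, two-sided 5%, dropout up to 10% and power above 85%. The response rates and within-participant correlation are not disclosed, so this can be neither confirmed nor refuted.

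- Single-timepoint test of two proportions, assumed rimegepant rates of 30% to 60%: power is 82.2% to 86.1% with all 575 analysed, and 78.1% to 82.4% after 10% dropout.
- Mean of three monthly responses, variance factor (1 + 2ρ)/3, 10% dropout, assumed rimegepant rates of 40% to 50%: about 94% to 95% at ρ = 0.4, 89% to 90% at 0.6, 87% at 0.7, 84% to 85% at 0.8, and 79% at 1.

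The stated power is thus attainable if ρ is no more than about 0.7.

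**Loss of power from the exclusion.** Assume 44% against 56%, ρ = 0.6 and 10% dropout.

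- n per arm = 287.5 × 0.9 = 258.75.
- Variance factor = (1 + 1.2)/3 = 0.733.
- SE = √[0.733 × (0.56×0.44 + 0.44×0.56)/258.75] = 0.0374.
- Power = Φ(0.12/0.0374 − 1.96) = 89.5%.

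Multiplying n by (1 − share excluded) gives:

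| Assumed share with one product only | About how many of 575 | Power |
|---|---|---|
| 0% | 0 | 89.5% |
| 0.5% | 3 | 89.3% |
| 1% | 6 | 89.2% |
| 2% | 12 | 88.9% |
| 5% | 29 | 87.9% |

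**Shift in a response rate.** One participant is 1/288 = 0.35% of an arm. If three observed non-responders are dropped from one arm of 288 with a true 50% rate, that rate becomes 144/285 = 50.5%, against 144/288 = 50.0%.

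More generally, if a share x of one arm is dropped and all are non-responders, the rate p rises by p/(1 − x) − p. For p between 40% and 50% the rise is 0.2 to 0.3 points at x = 0.5%, 0.4 to 0.5 at 1%, 0.8 to 1.0 at 2%, and 2.1 to 2.6 at 5%. The design difference is 12 points.

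**The case against.** The best counter-argument is that SAP 5.1 only clarifies a loose term. Protocol 4.1.3 describes the first dose at Visit 3 as two injections plus one tablet, so a dose of study intervention could mean the pair. Protocol section 9 presents itself as a summary, and the final SAP is the official version. That reading is possible, but it sits badly with the protocol's own definition of study intervention and with SAP 5.2, which treats either product as exposure.

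Several points about size do stand:

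- A dose of each product at any time is enough. Someone who misses the tablet on site and takes one at home later is still in the set.
- Both first doses are given on site and the first tablet is supervised, so cases should be rare.
- SAP Table F requires a baseline and a post-baseline observation, and SAP 18.1.2 sets a month with 50% or less diary compliance to missing. Someone who leaves at Visit 3 adds nothing under either definition.
- The 0.5-point shift is a worst case: all three in one arm, all observed non-responders, none in the other arm.
- Nothing in the documents shows that completing the first pair of doses would differ by arm. Both arms receive the same number of injections and tablets under blind, and set membership is agreed before unblinding. That agreement guards against selective choice by analysts, but not against selection by what happened at dosing.

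It is also true that the protocol's set conditions on dosing after randomisation, so restoring it does not give an all-randomised set. It does remove the exclusion of people whose dosing has already begun.

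**Conclusion.** The concern holds as a minor point. The SAP's ITT set is narrower than the protocol's, the change is not declared in SAP 3.3, and it can remove randomised, treated and followed participants from the primary analysis, contrary to the treatment-policy estimand.

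The expected effect is small: about 0.3 points of power at 1% excluded, and at most about 0.5 points on one arm's response rate if three non-responders are lost from it. These figures rest on an assumed count of 0 to 6 of 575 and on assumed response rates and correlation; the documents supply none of them. The point is unlikely to decide the trial. The case for acting is agreement between the two documents on the primary population, together with removal of an avoidable exclusion.

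**What to change.** Align SAP 5.1 with protocol 9.2: include every randomised participant given one or more doses of either product, and analyse each in the arm to which they were randomised. This is one line of text and leaves the planned 575 and the stated power as they are.

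If the sponsor prefers the narrower set, it should declare and justify it in SAP 3.3, report the number excluded in each arm, and add a sensitivity analysis on the protocol's set. That costs more than the correction.
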